## 2.1.2 Exclusion Criteria

- 2.1.2.1 Participants who have had chemotherapy, immunotherapy or radiotherapy within 4 weeks or treatment with rituximab/Ruxience within last 3 months prior to initiation of treatment.
- 2.1.2.2 Participants who are receiving any other investigational agents.
- 2.1.2.3 Breastfeeding within the projected duration of the study, starting with the screening visit through 6 months after the last dose of rituximab/Ruxience. Pregnant women are excluded from this study because moxetumomab pasudotox-tdfk and rituximab/Ruxience are agents with the potential for teratogenic or abortifacient effects. Because there is an unknown but potential risk for adverse events in nursing infants secondary to treatment of the mother with moxetumomab pasudotox-tdfk and rituximab/Ruxience, breastfeeding should be discontinued if the mother is treated with moxetumomab pasudotox-tdfk and rituximab/Ruxience.
- 2.1.2.4 Participants with known brain metastases should be excluded from this clinical trial because of their poor prognosis and because they often develop progressive neurologic dysfunction that would confound the evaluation of neurologic and other adverse events.
- 2.1.2.5 Uncontrolled intercurrent illness including, but not limited to, ongoing or active infection, symptomatic congestive heart failure, unstable angina pectoris, cardiac arrhythmia, uncontrolled hypertension, uncontrolled pulmonary infection, pulmonary edema or psychiatric illness/social situations that would limit compliance with study requirements.
- 2.1.2.6 Participants with retinal or choroidal detachment.
- 2.1.2.7 Positive for Hepatitis B core antibody or surface antigen unless the participant is on Tenofovir or Entecavir and Hepatitis B Viral deoxyribonucleic acid (DNA) load is <2000 IU/mL
- 2.1.2.8 Active second malignancy requiring treatment other than minor resection of indolent

cancers like basal cell and squamous skin cancers.

- 2.1.2.9 Human immunodeficiency virus (HIV)-positive participants unless taking appropriate anti-HIV medications with a CD4 count of > 200. Otherwise, there may be an increased risk of lethal infections when temporarily suppressing normal B-cells.
- 2.1.2.10 History of an allogeneic bone marrow transplant.
- 2.1.2.11 Participants with a history of both thromboembolism and known congenital hypercoagulable conditions.
- 2.1.2.12 Radioimmunotherapy within 2 years prior to enrollment in the study.
- 2.1.2.13 Participants with history of thrombotic microangiopathy or thrombotic microangiopathy/HUS.
- 2.1.2.14 Participants with corrected QT interval (Frederica) elevation > 500 msec (manually overread by medically qualified person) based on at least two separate 12-lead ECGs.
- 2.1.2.15 Participants on high dose estrogen (defined as > 0.625 mg/day of an estrogen compound).
- 2.1.2.16 Oxygen saturation at rest < 88% measured by pulse oximetry or PaO2  $\le 55$  mm Hg.
- 2.1.2.17 Participants with life expectancy of less than 6 months.
- 2.1.2.18 Participants with clinical evidence of disseminated intravascular coagulation (Grade 3-4).
- 2.1.2.19 Participants with < 50% of predicted forced expiratory volume (FEV1) or < 50% of predicted diffusing capacity for carbon monoxide, corrected for hemoglobin concentration and alveolar volume (DLCO). Note: Participants with no prior history of pulmonary illness are not required to have pulmonary function testing (PFT). Forced expiratory volume will be assessed after bronchodilator therapy.

## 2.1.3 Recruitment Strategies

Recruitment of participants from outside NIH is facilitated by multiple ongoing trials at NIH. Many participants find about NIH trials from NIH websites, such as https://clinicaltrials.gov/ or NIH social media, or from other participants through social media, and neither the PI nor the research staff interacts with these sites. The Hairy Cell Leukemia Foundation, which refers HCL and HCLv participants to trials, has an active website and is a significant source of recruitment. Finally, participants who are relapsing from NIH protocols for early HCL/HCLv may be eligible for NIH trials for relapsed HCL/HCLv.

## 2.2 SCREENING EVALUATION

Screening evaluation testing/procedures are conducted under the separate screening protocol, 01-C-0129 (Eligibility Screening and Tissue Procurement for the NIH Intramural Research Program Clinical Protocols). See also Study Calendar in Section 3.4.

- 2.2.1.1 Laboratory evaluation (needed for eligibility)
  - 2.2.1.1.1 Within 6 months before starting drug, provided >4 weeks after chemotherapy, immunotherapy or radiotherapy prior to entering the study:
  - Bone marrow biopsy (BMBx) with IHC for CD20 and CD3.

Version Date: 04/16/2025

• BMBx is not needed if participants can provide test slides to be read at the Clinical Center along with reports. In case slides and reports are not available, fresh biopsy will be done.

## 2.2.1.1.2 Within 6 months before starting drug

- Hepatitis B (HBcAB and HBsAg), and HIV test
- CD4/CD8 (only in HIV participants)

## 2.2.1.1.3 Within 4 weeks before starting drug

- CBC with differential
- Chemistries including acute care panel (sodium, potassium, chloride, CO2, glucose, creatinine, and BUN), mineral panel (calcium, magnesium, phosphorus and albumin), hepatic panel (AST, ALT, total and direct bilirubin, alkaline phosphatase), total protein, creatine kinase (CK), uric acid, LDH, urinalysis, D-Dimer, Ferritin, Fibrinogen, PT/INR, PTT, amylase, lipase, GGT, IgA, IgG, IGM, CRP, TBNK, haptoglobin, Lipid panel (cholesterol, triglycerides, HDL, LDL), TSH, FT4, FT3, T4, T3,IFE.
- Flow cytometry of blood
- EKG
- History & Physical with documented performance status
- Vital signs including ambulatory oxygen saturation by pulse oximetry. Pulmonary function test (PFTs) if measuring PaO2

# 2.2.1.1.4 Within 3 days before starting drug

Pregnancy test (urine or serum). Women of childbearing potential must have a negative pregnancy test

#### 2.3 PARTICIPANT REGISTRATION AND STATUS UPDATE PROCEDURES

Registration and status updates (e.g., when a participant is taken off protocol therapy and when a participant is taken off-study) will take place per CCR SOP ADCR-2, CCR Participant Registration & Status Updates found at: https://nih.sharepoint.com/sites/NCI-CCR-OCD-Communications/SitePages/OEC-Administrative---Clinical-Research-(ADCR).aspx?Mode=Edit.

# 2.3.1 Treatment Assignment Procedures

## Cohort

Number	Name	Description
1	HCL/HCLv	Participants with HCL and HCLv

Version Date: 04/16/2025

#### Arm

Number	Name	Description
1	Arm 1 – Dose escalation	Treatment with moxetumomab pasudotox-tdfk and rituximab (participants 1-13)
2	Arm 2 – Dose expansion	Treatment with moxetumomab pasudotox-tdfk and Ruxience (participants 14-26)

# **Arm Assignment**

Participants in cohort 1 will be directly assigned to arm 1 or 2 in sequential fashion.

#### 2.4 BASELINE EVALUATION

See also Section 3.4, Study Calendar and Section 2.2, Screening Evaluation

## 2.4.1 Within 6 months before drug

- MRI Cervical and Thoracic (C- and T-) Spine to correlate the status of the BMBx with the vertebral bone marrow aspiration (BMA) signal by MRI. May be cancelled at the discretion of the PI, including if participant unable to get MRI at NIH and not covered by insurance outside NIH.
- CT Neck-pelvis or MRI
- Abdominal Ultrasound (U/S) will be done to exclude lymph nodes potentially impacting the biliary tree
- Echo, PFTs, stress test
- BMA for FACS and PCR (if evaluable). Blood PCR should be done at the same time as BMA PCR in the CLIA certified laboratory at the Laboratory of Pathology, CCR/NCI. HLA test (May be done any time before initiation of study therapy)

## 2.4.2 Within 4 weeks before drug

- PaxGene RNA & DNA
- 24 hour urine for protein and creatinine clearance
- Serum tube for tumor markers and antibodies
- Peripheral blood mononuclear cells (PBMCs) in Sodium heparin tubes

## 3 STUDY IMPLEMENTATION

## 3.1 STUDY DESIGN

This is a Phase 1 trial, two-arm, non-randomized trial involving the administration of moxetumomab pasudotox-tdfk 30-40 mcg/kg iv and rituximab/Ruxience 375 mg/m² iv, 50-400 mg/hr. The purpose of the rituximab/Ruxience is to decrease the HCL tumor burden, allowing the

Version Date: 04/16/2025

63 kDa immunotoxin to reach all the malignant cells, thereby facilitating tumor eradication, and prevention of neutralization of the immunotoxin by the immune system, through the action of rituximab/Ruxience on normal B-cells. To allow sufficient time for the rituximab/Ruxience to act prior to moxetumomab pasudotox-tdfk, in the first cycle, rituximab/Ruxience will be given on day -2 followed by moxetumomab pasudotox-tdfk on days 1, 3 and 5. Thus on cycle 1 only, moxetumomab pasudotox-tdfk will begin on the 3rd day after rituximab/Ruxience. On subsequent cycles, spaced ~ 4 weeks (as few as 25 days) apart, rituximab/Ruxience will begin on day 1 and moxetumomab pasudotox-tdfk on days 1, 3 and 5. Participants will receive up to 4 cycles past documentation of CR without MRD, up to a maximum of 8 cycles which means, no participant in this trial will receive more than 8 cycles.

#### **3.1.1** Schema

## Cycle 1:

DAY -2	Day -1	Day 0	DAY 1	Day 2	DAY 3	Day 4	DAY 5	Day ≥26
Rituximab /Ruxience			Moxetumomab pasudotox-tdfk		Moxetumomab pasudotox-tdfk		Moxetumomab pasudotox-tdfk	(next cycle)

## **Cycles 2-8:**

Day -2	Day -1	Day 0	DAY 1	Day 2	DAY 3	Day 4	DAY 5	Day ≥26
			Rituximab/Ruxience					(next cycle)
			Moxetumomab pasudotox- tdfk		Moxetumomab pasudotox- tdfk		Moxetumomab pasudotox- tdfk	

# 3.1.2 Dose Limiting Toxicity

Dose limiting toxicity (DLT) is defined as all treatment related Grade 3 and greater AEs occurring from the initiation of moxetumomab pasudotox-tdfk therapy to within 30 days after the last dose of moxetumomab pasudotox-tdfk treatment. For example, grade >3 cytokine release syndrome, and failure to complete cycle 1 due to toxicity is considered DLT.

Exceptions to DLT include:

- Hematologic toxicity grade 3, or grade 4 resolving within 4 weeks.
- Hematologic toxicity managed with transfusion and/or other support would not constitute DLT.
- Grade 3-4 lymphopenia, leukopenia, or CD4 reductions.
- Grade 3 gastrointestinal toxicity resolving within 72 hours.

- Transaminase and alkaline phosphates elevations grade 3 resolving within 4 weeks.
- Bilirubin elevations associated with Gilbert's syndrome, i.e. total/direct bilirubin ratio ≥4.
- Electrolyte or mineral abnormalities which are grade 3-4, resolving within 4 weeks.
- Grade 3 proteinuria, and fever
- Lipid elevations grade 3 or grade 4 resolving within 4 weeks
- Grade 3 HUS, including HUS-related grade 1-2 creatinine, will not be considered DLT if it resolves within 2 weeks to grade 0-1 creatinine, and is not associated with significant complications including bleeding or need for dialysis or plasmapheresis.
- Allergic reactions to rituximab/Ruxience prevented by desensitization.
- Dosing of both agents must be delayed for any grade 3-4 infection at least possibly related to either drug, and if not resolved despite a 4-week delay will be considered DLT requiring removal from treatment.
- Other isolated grade 3 laboratory abnormalities (not related to CLS or HUS) without clinical signs or symptoms and not associated with clinical sequalae requiring therapeutic intervention.

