- 1. End of treatment visit will occur 28-42 days after 1st dose of last cycle.
- All participants will be offered the opportunity to complete an NIH advance directives form (Section 12.3). This should be done preferably at baseline but can be done at any time during the study. The completion of the form is strongly recommended but not required.
- Within 4 weeks prior to enrollment, could be combined with pre cycle 1. Only anti-moxetumomab pasudotox-tdfk antibodies will be assessed.
- 4. CBC + Diff should be done every 3 months until 2.5y after EOT, then every 6 months.
-  Follow-up time points not requiring restaging are 1, 2 and 3.5 years after EOT, then every 2 years
- 6. Restaging requiring imaging, labs (and bone marrow if CR suspected) is 1.5 and 2.5 years after EOT, then every 2 years.
- Within 6 months of initiation of study therapy provided within 4 weeks after last therapy. Baseline HLA may be done anytime.
- PK and PK bioassay Time points: On days 1 and 5 of cycles 1,2,3,5,7. For cycles 1 and 2: pre, and immediately post, +/- 8 min, then 30+/-10, 60+/-15, 180+/-20,, and 360+/-50 minutes after moxetumomab pasudotox-tdfk end of infusion; On cycles 3, 5, and 7: pre and post infusion, 1-8 min; on cycles 4, 6, and 8 no PK will be drawn. Each ~6cc in K2EDTA tubes.
- 9. CT Neck-Pelvis is done at baseline to identify sites of disease, including spleen, and at EOT and restaging points MRI of these sites may be substituted. In asplenic participants without baseline sites of disease, MRI of the abdomen may be done at restaging time points. The entire neck to pelvis CT need not be repeated if the disease (splenomegaly) was contained within just the abdominal or abdominal-pelvis levels of the CT. Pre-cycle scans will only be performed if participant is being restaged.
- 10. Deviations on post-EOT time points may be +/- 2 months until 2.5 years and +/- 4 months thereafter.
- Chemistries includes sodium, potassium, chloride, bicarbonate, creatinine, glucose, blood urea nitrogen (BUN), albumin, calcium, magnesium, phosphorus, AST (SGPT), ALT (SGOT), total bilirubin, direct bilirubin, lactate dehydrogenase (LDH), total protein, alkaline phosphatase, creatine kinase (CK or CPK), and uric acid. Except on day 15. Day 15 only acute care panel along with CBC with c diff and urine analysis will be required.
- 12. Optional when not performed at NIH
- 13. +/-1 day,

Version Date: 04/16/2025

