## 3.6 CRITERIA FOR REMOVAL FROM PROTOCOL THERAPY AND OFF STUDY CRITERIA

Prior to removal from the study, effort must be made to have all participants complete a safety visit approximately 28-42 days following the last dose of study therapy.

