## 6 DATA COLLECTION AND EVALUATION

#### 6.1 DATA COLLECTION

The PI will be responsible for overseeing entry of data a 21 CFR Part 11-compliant data capture system provided by the NCI CCR and ensuring data accuracy, consistency and timeliness. The principal investigator, associate investigators/research nurses and/or a contracted data manager will assist with the data management efforts. Primary and final analyzed data will have identifiers so that research data can be attributed to an individual human subject participant.

All adverse events, including clinically significant abnormal findings on laboratory evaluations, regardless of severity, will be followed until return to baseline or stabilization of event.

Document AEs from the first study intervention, Study Day 1, through the end of treatment. After 30 days, only adverse events which are serious and related to the study intervention need to be recorded.

An abnormal laboratory value will be recorded in the database as an AE **only** if the laboratory abnormality is characterized by any of the following:

- Results in discontinuation from the study
- Is associated with clinical signs or symptoms
- Requires treatment or any other therapeutic intervention
- Is associated with death or another serious adverse event, including hospitalization.
- Is judged by the Investigator to be of significant clinical impact
- If any abnormal laboratory result is considered clinically significant, the investigator will provide details about the action taken with respect to the test drug and about the participant's outcome.

**End of study procedures:** Data will be stored according to HHS, FDA regulations, and NIH Intramural Records Retention Schedule as applicable.

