# 8.4.3.2 Reporting of Adverse events (AEs)

AEs for new primary malignant tumors reported during a study should generally be assessed as serious AEs. If no other seriousness criteria apply, the 'important medical event' criterion should be used. In certain situations, however, medical judgement on an individual event basis should be applied to clarify that the primary malignant tumor event should be assessed and reported as a non-serious AE. For example, if the tumor is included as medical history and progression occurs during the study, but the progression does not change treatment and/or prognosis of the malignant tumor, the AE may not fulfil the attributes for being assessed as serious, although reporting of the progression of the malignant tumor as an AE is valid and should occur. Also, some types of malignant tumors, which do not spread remotely after a routine treatment that does not require hospitalization, may be assessed as non-serious; examples include Stage I basal cell carcinoma and Stage IA1 cervical cancer removed via cone biopsy.

Non-serious adverse events and SAEs will be collected from the time consent is given, throughout the treatment period and up to and including the 30-day follow-up period. After withdrawal from treatment, subjects must be followed up for all existing and new AEs for 30 calendar days after the last dose of trial drug and/or until event resolution. All new AEs occurring during that period must be recorded (if SAEs, then they must be reported as indicated in Sections 8.3 and 8.4.1). All study-related toxicities/ SAEs must be followed until resolution, unless in the Investigator's opinion, the condition is unlikely to resolve due to the patient's underlying disease.

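### Read literally, the DLT window opens only at the first moxetumomab dose, so a severe antibody reaction on day -2 that does not stop cycle 1 is missed by the count deciding the primary safety endpoint

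*Combined protocol and SAP*

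**What the plan says.** Section 3.1.2 limits DLTs to treatment-related events of grade 3 or higher "occurring from the initiation of moxetumomab pasudotox-tdfk therapy to within 30 days after the last dose of moxetumomab pasudotox-tdfk treatment". Section 3.1 sets the order of dosing: "in the first cycle, rituximab/Ruxience will be given on day -2 followed by moxetumomab pasudotox-tdfk on days 1, 3 and 5". In later cycles both agents are given on day 1, so the antibody dose then falls inside the window.

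Section 10.4.2 judges the primary safety endpoint by the DLT count: 10 participants treated, with no more than 2 DLTs. Section 10.2 attaches a one-sided 90% upper bound of 45.0% to 2/10. The objective in Sections 1.1.1 and 10.1 is the safety and toxicity of moxetumomab together with the antibody.

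Four other statements bear on when counting starts:
- Section 3.1.2 gives as examples "grade >3 cytokine release syndrome, and failure to complete cycle 1 due to toxicity is considered DLT", without tying them to one drug, and lists among the exceptions "Allergic reactions to rituximab/Ruxience prevented by desensitization".
- Section 3.1.3.1 says DLTs are evaluated throughout study therapy, and Section 10.3.1 makes participants evaluable for toxicity from their first treatment.
- Section 6.1 says: "Document AEs from the first study intervention, Study Day 1, through the end of treatment".
- Section 8.4.3.2 says: "Non-serious adverse events and SAEs will be collected from the time consent is given". Section 8.2 starts SAE reporting at the first administration of investigational product.

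**The concern.** The question is whether the combination is safe, and the combination begins with the antibody on day -2. A grade 3 or higher reaction to that infusion, managed so that moxetumomab can start on day 1, predates the window. It could be recorded as an adverse event and still not enter the count that decides the endpoint.

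The protocol takes this infusion seriously. Section 1.2.2 says rituximab cannot be safely started without prophylactic steroid when tumor burden is significant. The Study Calendar schedules a cytokine panel on days -2 and -1. Yet cytokine release on those days, which Section 3.1.2 names as a kind of DLT, would come before counting begins.

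The wording also affects a statement already made. Section 3.1.4 reports no DLT among the first 12 participants in setting out the expansion by 13 more. A reader cannot tell whether that covers days -2 to 0.

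**Working it through.** **The plan's own figure.** The exact (Clopper-Pearson) one-sided 90% upper bound on 2/10 is the 0.90 quantile of Beta(3, 8) = 0.4496, that is 45.0%. It reproduces. The window does not alter this bound. It alters which events are counted toward it.

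**Is the early period inside the DLT window?**
- By the definition in 3.1.2: no. The window starts on cycle 1 day 1.
- By the desensitization exception in 3.1.2: probably yes. There would be little need to exempt some antibody reactions if none could count, although antibody doses in later cycles give the exception some work to do.
- By 3.1.3.1 and 10.3.1: yes, since study therapy and first treatment begin with the antibody.
- By the cycle 1 completion clause in 3.1.2: arguably yes, but only if toxicity prevents completion. The clause is offered as an example of the definition, so one could argue that it inherits the window.

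What remains uncovered is a qualifying event on days -2 to 0 after which cycle 1 is still completed.

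**When does adverse event collection start?** Section 6.1 equates the first intervention with Study Day 1, although the first study drug is given on day -2. Section 8.4.3.2 starts at consent. Section 8.2 starts SAE reporting at first investigational product, but refers back to 6.1 for the recording period.

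**How long is the gap?** Section 3.2.2 puts the antibody two days before day 1. Section 3.1 starts moxetumomab on the third day after it, and the schema in 3.1.1 shows a Day 0, which also makes three days.

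**Illustration of size.** Let p be the chance of a DLT inside the window and q the chance of an otherwise qualifying event between the first antibody dose and day 1. Neither is given for this population. Assume p = 10%, q between 1% and 20%, and independence.

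With early events counted, the chance per participant is r = 1 - (1 - p)(1 - q). The chance of meeting the rule is P(X ≤ 2) for X ~ Binomial(10, r).

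| q | r | P(at most 2 of 10) |
|---|---|---|
| not counted | 0.100 | 0.930 |
| 1% | 1 - 0.90 × 0.99 = 0.109 | 0.913 |
| 5% | 1 - 0.90 × 0.95 = 0.145 | 0.833 |
| 10% | 1 - 0.90 × 0.90 = 0.190 | 0.708 |
| 20% | 1 - 0.90 × 0.80 = 0.280 | 0.438 |

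The first row is 0.349 + 0.387 + 0.194 = 0.930 for 0, 1 and 2 events. At q = 5% the terms are 0.209 + 0.354 + 0.270 = 0.833.

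The only serious-reaction figure in the documents is in Section 14.2.2: below 1%, in rheumatoid arthritis. At that level the effect is small. It becomes material at about 5% or more.

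**The case against.** Moxetumomab is the escalated agent and the antibody dose is fixed, so tying the window to moxetumomab is a recognizable phase 1 choice. That would be a full answer if the endpoint were the tolerability of moxetumomab given after the antibody. The stated endpoint is the safety of the combination, and other sections do not follow the narrower window.

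Four stronger readings are tempting, and the documents do not support them.

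- *A participant who never reaches moxetumomab because of a day -2 reaction has no DLT.* The completion clause in 3.1.2 arguably makes that a DLT.
- *The riskiest infusion of the combination is outside the primary endpoint.* The documents show the first antibody infusion to be the antibody dose most prone to acute reactions (27% after the first, 9% after the second, in rheumatoid arthritis). The hemolytic uremic and capillary leak syndromes in Section 1.2.1 were reported with moxetumomab. Section 10.4.4 also covers lesser toxicities of each agent. It is the DLT count that misses the event, not all safety reporting.
- *About seven participants would have uncounted events (27% of 26).* The 27% is any grade and from another disease. Section 3.1.2 exempts grade 3 fever, and the same source puts serious reactions below 1%. The limit of 2 applies per 10 participants, not per 26.
- *The far end of the window is unobserved.* Section 3.4 says "End of treatment visit will occur 28-42 days after 1st dose of last cycle", so the visit can fall on day 29, 24 days after the day 5 dose. But Section 8.4.3.2 requires adverse event follow-up for 30 calendar days after the last dose, the calendar footnotes require continuous monitoring, and Section 3.6 asks participants to "complete a safety visit approximately 28-42 days following the last dose of study therapy". This is largely handled.

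One objection stands and shapes the fix. Section 3.3 removes from therapy anyone with a DLT as defined in 3.1.2, and Sections 3.1.3 and 10.2 tie dose assignment and accrual to DLTs. Simply redefining DLT would therefore change clinical management.

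**Conclusion.** The concern holds in a limited form and should be fixed. The literal window omits qualifying events on days -2 to 0 that do not stop cycle 1, from the count that decides the primary endpoint. It also conflicts with other text on when toxicity is evaluated and recorded, so two assessors could classify the same event differently.

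Any bias is downward, toward calling the combination safe. Its size is unknown: with an assumed 10% in-window rate, the chance of meeting the rule is overstated by 0.930 - 0.913 = 0.017 if q is 1%, and by 0.930 - 0.833 = 0.097 if q is 5%. Both rates and independence are assumptions. A reader might infer that DLTs have in fact been undercounted, but the documents report no uncounted day -2 event, and the 45.0% bound is unaffected.

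**What to change.** For the primary endpoint count and its reporting, count otherwise qualifying events from the first dose of either agent, which is day -2 of cycle 1. Write this as an endpoint definition separate from the DLT definition that governs treatment. Correct the start in Section 6.1 to match, and bring Sections 8.2 and 8.4.3.2 into line. Re-tabulate participants already treated on this basis, and confirm or revise the statement in Section 3.1.4 that none had a DLT.

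Reconcile Sections 3.1, 3.1.1, 3.1.2, 3.1.3.1, 3.2.2, 6.1, 8.2, 8.4.3.2, 10.3.1 and 10.4.2, including the two-day versus three-day gap. Whether an event before day 1 also leads to removal from therapy (Section 3.3), or enters the dose and accrual rules (Sections 3.1.3 and 10.2), is a separate clinical decision for the sponsor.

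The cost is wording and a recount, since assessments on days -2 and -1 are already scheduled. The downside is that the count may rise slightly.
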